7.2 Method of Treatment Assignment

After the participant's eligibility is established and informed consent has been obtained, the participant will be enrolled and a number will be assigned through an interactive voice response system (IVRS). Also, the IVRS will be used to manage enrollment of participant subgroups. Specific instructions and procedures for using IVRS will be provided to the investigational site in a separate document/ manual.

The investigator (or designee) will register the participant for enrollment by following the enrollment procedures established by BMS. The following information is required for enrollment:

- Date of informed consent
- Date of birth
- Gender at birth
- Confirmed RCC histology
- Confirmed presence or absence of brain metastases
- Performance Status

7.3 Blinding

This is an open-label study, blinding procedures are not applicable.

7.4 Dosage Modification

Dose reductions or dose escalations of nivolumab or ipilimumab are not permitted.

7.4.1 Study Treatment Dose Delay Criteria

Study treatment administration should be delayed for the following:

- Grade 2 non-skin, drug-related adverse event, with the exception of fatigue
- Grade 2 drug-related creatinine, AST, ALT and/or Total Bilirubin abnormalities
- Grade 3 skin, drug-related adverse event
- Grade 3 drug-related laboratory abnormality, with the following exceptions:
 - Grade 3 lymphopenia or asymptomatic amylase or lipase does not require dose delay
 - Grade ≥ 3 AST, ALT, Total Bilirubin will require dose discontinuation (see [Section 8.1.1](#))
- Any adverse event, laboratory abnormality, or intercurrent illness which, in the judgment of the investigator, warrants delaying the dose of study medication.

Participants who require delay of study treatment should be re-evaluated weekly or more frequently if clinically indicated and resume nivolumab dosing when re-treatment criteria are met.

During Cycles 1 and 2, both nivolumab and ipilimumab must be delayed at the same time.

Because of the potential for clinically meaningful nivolumab or ipilimumab-related AEs requiring early recognition and prompt intervention, management algorithms have been developed for

suspected pulmonary toxicity, GI, hepatotoxicity, endocrinopathy, skin toxicity, neurological toxicity and renal toxicity.

In order to standardize the management of overlapping adverse event management algorithms present in both the BMS-936558 (nivolumab) and ipilimumab IB (**GI, hepatic, and endocrine** algorithms), the recommendations are to follow the BMS-936558 (nivolumab) IB adverse event algorithms as opposed to the ipilimumab IB algorithms.

The algorithms recommended for utilization in are included in [Appendix 8](#).

7.4.2 Treatment of Nivolumab or Ipilimumab Related Infusion Reactions

Since nivolumab and ipilimumab contain only human immunoglobulin protein sequences, each is unlikely to be immunogenic and induce infusion or hypersensitivity reactions. However, if such a reaction were to occur, it might manifest with fever, chills, rigors, headache, rash, pruritus, arthralgias, hypotension, hypertension, bronchospasm, or other allergic-like reactions. All Grade 3 or 4 infusion reactions should be reported within 24 hours to the BMS Study Medical Monitor and reported as an SAE if it meets the criteria. Infusion reactions should be graded according to NCI CTCAE (Version 4) guidelines.

Treatment recommendations are provided below and may be modified based on local treatment standards and guidelines, as appropriate:

For Grade 1 symptoms: (mild reaction; infusion interruption not indicated; intervention not indicated):

- Remain at bedside and monitor participant until recovery from symptoms. The following prophylactic premedications are recommended for future infusions: diphenhydramine 50 mg (or equivalent) and/or acetaminophen/paracetamol 325 to 1000 mg at least 30 minutes before additional nivolumab administrations.

For Grade 2 symptoms: (moderate reaction required therapy or infusion interruption but responds promptly to symptomatic treatment (eg, antihistamines, non-steroidal anti-inflammatory drugs, narcotics, corticosteroids, bronchodilators, IV fluids); prophylactic medications indicated for ≤ 24 hours):

- Stop the nivolumab or ipilimumab infusion, begin an IV infusion of normal saline, and treat the participant with diphenhydramine 50 mg IV (or equivalent) and/or acetaminophen/paracetamol 325 to 1000 mg; remain at bedside and monitor participant until resolution of symptoms. Corticosteroid and/or bronchodilator therapy may also be administered as appropriate. If the infusion is interrupted, then restart the infusion at 50% of the original infusion rate when symptoms resolve; if no further complications ensue after 30 minutes, the rate may be increased to 100% of the original infusion rate. Monitor participant closely. If symptoms recur, then no further nivolumab or ipilimumab will be administered at that visit.
- For future infusions, the following prophylactic premedications are recommended: diphenhydramine 50 mg (or equivalent) and/or acetaminophen/paracetamol 325 to 1000 mg

should be administered at least 30 minutes before nivolumab infusions. If necessary, corticosteroids (up to 25 mg of hydrocortisone or equivalent) may be used.

For Grade 3 or 4 symptoms: (severe reaction, Grade 3: prolonged [ie, not rapidly responsive to symptomatic medication and/or brief interruption of infusion]; recurrence of symptoms following initial improvement; hospitalization indicated for other clinical sequelae (eg, renal impairment, pulmonary infiltrates). Grade 4: Life-threatening; pressor or ventilatory support indicated):

- Immediately discontinue infusion of nivolumab or ipilimumab. Begin an IV infusion of normal saline and treat the participant as follows: Recommend bronchodilators, epinephrine 0.2 to 1 mg of a 1:1000 solution for subcutaneous administration or 0.1 to 0.25 mg of a 1:10,000 solution injected slowly for IV administration, and/or diphenhydramine 50 mg IV with methylprednisolone 100 mg IV (or equivalent), as needed. Participant should be monitored until the Investigator is comfortable that the symptoms will not recur. Study drug will be permanently discontinued. Investigators should follow their institutional guidelines for the treatment of anaphylaxis. Remain at bedside and monitor participant until recovery of the symptoms.

In case of late-occurring hypersensitivity symptoms (eg, appearance of a localized or generalized pruritus within 1 week after treatment), symptomatic treatment may be given (eg, oral antihistamine or corticosteroids).

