8.1.1 Dose Discontinuation

Study treatment should be permanently discontinued for the following:

- Any Grade 2 drug-related uveitis, eye pain or blurred vision that does not respond to topical therapy and does not improve to Grade 1 severity within the re-treatment period OR requires systemic treatment
- Any Grade 3 non-skin, drug-related adverse event lasting > 7 days, or recurs with the following exceptions for laboratory abnormalities, diarrhea, colitis, neurologic toxicity, drug-related

uveitis, pneumonitis, bronchospasm, hypersensitivity reactions, infusion reactions, and endocrinopathies:

- Grade 3 drug-related diarrhea, colitis, neurologic toxicity, uveitis, pneumonitis, bronchospasm, hypersensitivity reaction, or infusion reaction of any duration requires discontinuation
- Grade 3 drug-related endocrinopathies, adequately controlled with only physiologic hormone replacement do not require discontinuation. Adrenal insufficiency requires discontinuation regardless of control with hormone replacement.
- Grade 3 drug-related laboratory abnormalities do not require treatment discontinuation except:
 - ◆ Grade 3 drug-related thrombocytopenia > 7 days or associated with bleeding requires discontinuation
 - ◆ Any drug-related liver function test (LFT) abnormality that meets the following criteria require discontinuation:
 - Grade ≥ 3 drug-related AST, ALT or Total Bilirubin requires discontinuation*
 - Concurrent AST or ALT > 3 x ULN and total bilirubin > 2x ULN

* In most cases of Grade 3 AST or ALT elevation, study drug(s) will be permanently discontinued. If the investigator determines a possible favorable benefit/risk ratio that warrants continuation of study drug(s), a discussion between the investigator and the BMS Medical Monitor/designee must occur.

- Any Grade 4 drug-related adverse event or laboratory abnormality (including but not limited to creatinine, AST, ALT, or Total Bilirubin), except for the following events which do not require discontinuation:
 - Grade 4 neutropenia ≤ 7 days
 - Grade 4 lymphopenia or leukopenia or asymptomatic amylase or lipase
 - Isolated Grade 4 electrolyte imbalances/abnormalities that are not associated with clinical sequelae and are corrected with supplementation/appropriate management within 72 hours of their onset

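### Protocol 7.4.2 is internally inconsistent on the grade and later dosing of an infusion reaction that recurs after the infusion is restarted

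*Protocol*

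**What the plan says.** Three pieces of protocol text bear on the same event.

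- **7.4.2, Grade 2.** Grade 2 is a "moderate reaction required therapy or infusion interruption but responds promptly to symptomatic treatment". After interruption the instruction is "If the infusion is interrupted, then restart the infusion at 50% of the original infusion rate when symptoms resolve". On recurrence: "If symptoms recur, then no further nivolumab or ipilimumab will be administered at that visit". The second Grade 2 bullet begins "For future infusions, the following prophylactic premedications are recommended".
- **7.4.2, Grade 3 or 4.** The Grade 3 definition includes "recurrence of symptoms following initial improvement". The action for Grade 3 or 4 includes "Study drug will be permanently discontinued".
- **8.1.1.** "Grade 3 drug-related diarrhea, colitis, neurologic toxicity, uveitis, pneumonitis, bronchospasm, hypersensitivity reaction, or infusion reaction of any duration requires discontinuation".

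The opening of 7.4.2 adds three general statements. Infusion reactions are graded by CTCAE version 4. Grade 3 or 4 infusion reactions go to the Medical Monitor within 24 hours. The treatment advice consists of recommendations that may be adapted to local standards.

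**The concern.** Recurrence after restart is managed under the Grade 2 heading, but it also matches a criterion listed under the Grade 3 heading of the same section. The two headings differ in what they say about later visits. The Grade 2 text confines its stop to the current visit and then discusses future infusions. The Grade 3 text ends study treatment.

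Three things depend on which heading a site applies:

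- **Re-exposure.** Whether the participant is dosed again, within a treatment period of up to 24 months.
- **Reporting.** The 24-hour report to the Medical Monitor applies to Grade 3 or 4 infusion reactions, so the grade decides whether it is made.
- **Data.** The grade on the CRF, and whether the event counts as an AE leading to discontinuation. That count is an item in the safety-review package (Protocol 5.1.1, SAP 9.2.1), which informs decisions on further enrollment.

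**Working it through.** The plan states no figure on this point, so the check is to follow one event through the text.

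1. A participant has a moderate reaction that responds to treatment. The infusion is interrupted. This is Grade 2 under 7.4.2.
2. The infusion is restarted at half rate. The text allows this only after symptoms have resolved.
3. Symptoms return.
   - Under the Grade 2 paragraph, neither drug is given again that day. The paragraph mentions neither re-grading nor permanent discontinuation. The premedication bullet that follows covers later infusions for Grade 2 reactions generally and makes no exception for participants whose symptoms came back.
   - Under the Grade 3 definition, the event is a recurrence after improvement, because step 2 required resolution first. The action is permanent discontinuation. Under 8.1.1, if the event is drug-related, discontinuation is required whatever its duration. The 24-hour report is also due.
4. Size of the overlap: restart requires resolution, so every recurrence after restart follows an initial improvement. The two descriptions overlap for all such recurrences, not just unusual ones.
5. Search for a link: neither 7.4.2 nor 8.1.1 says that a recurrence on the Grade 2 pathway is re-graded, or that the Grade 2 sentence gives way to the Grade 3 rule.

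**Number of participants.** The documents give no rate of infusion reactions or of recurrence, so both rates below are assumptions, used only for scale.

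- Treated participants: 200 (Protocol 5.2).
- Assumed share with an interrupted Grade 2 reaction: 2% to 10%. 200 × 0.02 = 4; 200 × 0.10 = 20.
- Assumed share of those who recur on restart: 10% to 30%. 4 × 0.10 = 0.4; 20 × 0.30 = 6.

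The result is about 0.4 to 6 participants. The inconsistency in the text does not depend on this range.

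**Effect on the primary analysis.** Infusion reactions are not among the named IMAE categories in Protocol 9.2.1.1 and 10.3.2 or SAP 4.1 and 7.6.1.1. The sample-size and precision statements in Protocol 10.1 and SAP 5 use no infusion-reaction rate and are unaffected.

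**The case against.** A reader might infer that the section prescribes two opposite outcomes, with the Grade 2 text ordering a stop for one visit only and then a resumption of dosing. The documents do not support that reading. The Grade 2 sentence does not contain the word only, and it does not say that dosing resumes. Withholding drug on the day is compatible with stopping for good afterwards. The premedication bullet can be read as meant for participants whose restart succeeds.

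There is also a workable way to read the texts together. CTCAE grading is required, Grade 2 is limited to reactions that respond promptly, and recurrence is named under Grade 3. A site could therefore stop that day, re-grade the event and apply 8.1.1. That rule is mandatory and lacks the allowance for local modification found in 7.4.2. Section 9 requires immediate safety concerns to be discussed with the sponsor to determine whether treatment continues. Section 8.1 requires discontinuation when the investigator judges continued participation not to be in the participant's best interest. A site that recognises the recurrence as such a concern is not deciding alone.

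These points stand, and they limit the claim to an inconsistency that a careful site could resolve. They do not remove it. If every recurrence is Grade 3, the restriction to a single visit never describes the final outcome, yet the protocol places that restriction under Grade 2 and follows it with advice on future infusions. A site following the Grade 2 paragraph as written has grounds to dose again and to record Grade 2. The allowance for local modification does not settle the recorded grade. The Section 9 discussion depends on the site first seeing the event as an immediate safety concern.

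**Conclusion.** The point holds as an internal inconsistency in 7.4.2, and between its Grade 2 paragraph and 8.1.1. Recurrence after restart fits both the Grade 2 instruction and the Grade 3 definition, and nothing in the protocol says which governs. Grade, Medical Monitor reporting and later dosing can therefore differ between sites for the same reaction.

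The effect is on individual participants' safety management and on the consistency of safety data. It is not on the primary estimate: no named IMAE category and no stated precision changes. The number of participants is unknown and probably small. The range of 0.4 to 6 rests wholly on assumed rates, and its lower end is less than one person. The point is worth correcting because it concerns re-exposure after a recurrent reaction in a trial whose primary purpose is safety, and because the correction is cheap. Nothing here says which clinical rule is right.

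**What to change.** Reconcile three passages: the Grade 2 paragraph of 7.4.2, the Grade 3 definition and action in 7.4.2, and the infusion-reaction rule in 8.1.1. After the change, recurrence following a restart should have one stated grade and one stated consequence for later visits. The premedication bullet should say whether it applies to these participants. The same grade should be used for the 24-hour Medical Monitor report and on the CRF. Which outcome applies is for the clinical team to decide.

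The cost is protocol wording, by amendment or administrative letter, and a line in site training. It needs no additional participants, procedures or analyses.

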7.4.3 Management Algorithms for Immuno-Oncology Agents

Immuno-oncology (I-O) agents are associated with AEs that can differ in severity and duration than AEs caused by other therapeutic classes. Nivolumab and ipilimumab are considered immuno-oncology agents in this protocol. Early recognition and management of AEs associated with immuno-oncology agents may mitigate severe toxicity. Management Algorithms have been developed to assist investigators in assessing and managing the following groups of AEs:

- Gastrointestinal
- Renal
- Pulmonary
- Hepatic
- Endocrinopathy
- Skin
- Neurological

The above algorithms are found in both the nivolumab and ipilimumab Investigator Brochures, as well as in [Appendix 8](#).

[REDACTED]

[REDACTED]

[REDACTED]

[REDACTED]

[REDACTED]

[REDACTED]

[REDACTED]

[REDACTED]

[REDACTED]

[REDACTED]

[REDACTED]

[REDACTED]

[REDACTED]

[REDACTED]

7.8 Treatment After the End of the Study

At the conclusion of the study, participants who continue to demonstrate clinical benefit will be eligible to receive BMS supplied study treatment **for the maximum treatment duration specified in Sections 7.1.1 and 7.1.2.**

Study treatment will be provided via an extension of the study, a rollover study requiring approval by responsible health authority and ethics committee or through another mechanism at the discretion of BMS.

7.9 Treatment Beyond Progression

Accumulating evidence indicates a minority of participants treated with immunotherapy may derive clinical benefit despite initial evidence of PD. Participants will be permitted to continue study treatment beyond initial RECIST 1.1 defined PD as long as the following criteria are met:

- 1) Investigator-assessed clinical benefit
- 2) Tolerance of study drug
- 3) Stable performance status
- 4) Treatment beyond progression will not delay an imminent intervention to prevent serious complications of disease progression (eg, CNS metastases)
- 5) Participant provides written informed consent prior to receiving additional study treatment, using an ICF describing any reasonably foreseeable risks or discomforts, or other alternative treatment options.

The decision to continue treatment beyond initial progression should be discussed with the BMS medical Monitor and documented in the study records.

A radiographic assessment/ scan should be performed within 8 weeks of original PD to determine whether there has been a decrease in the tumor size, or continued PD. The assessment of clinical benefit should be balanced by clinical judgment as to whether the participant is clinically deteriorating and unlikely to receive any benefit from continued study treatment.

If the investigator feels that the participant continues to achieve clinical benefit by continuing treatment, the participant should remain on the trial and continue to receive monitoring according to the Time and Events Schedule (Section 2).

For the participants who continue study therapy beyond progression, further progression is defined as an additional 20% increase in tumor burden volume from time of initial PD. This includes an increase in the sum of all target lesions and/ or the development of new measurable lesions. Treatment should be discontinued permanently upon documentation of further disease progression

New lesions are considered measureable at the time of initial progression if the longest diameter is at least 10 mm (except for pathological lymph nodes which must have a short axis of at least 15 mm). Any new lesion considered non-measurable at the time of initial progression may become measureable and therefore included in the tumor burden volume if the longest diameter increases to at least 10 mm (except for pathological lymph nodes which must have a short axis of at least 15 mm).

Participants with global deterioration of health status (as determined by the investigator) who require discontinuation of treatment without objective evidence of disease progression at the time of treatment discontinuation should be reported as ‘symptomatic deterioration’. Every effort should be made to document objective progression (ie, radiographic confirmation) even after discontinuation of treatment.

8 DISCONTINUATION CRITERIA

8.1 Discontinuation from Study Treatment

Participants MUST discontinue investigational product (and non-investigational product at the discretion of the investigator) for any of the following reasons:

- Participant’s request to stop study treatment. Participants who request to discontinue study treatment will remain in the study and must continue to be followed for protocol specified follow-up procedures. The only exception to this is when a participant specifically withdraws consent for any further contact with him/her or persons previously authorized by participant to provide this information
- Any clinical adverse event (AE), laboratory abnormality or intercurrent illness which, in the opinion of the investigator, indicates that continued participation in the study is not in the best interest of the participant
- Termination of the study by Bristol-Myers Squibb (BMS)

- Loss of ability to freely provide consent through imprisonment or involuntarily incarceration for treatment of either a psychiatric or physical (eg, infectious disease) illness
- Additional protocol specified criteria for discontinuation (see Section 8.1.1)

Refer to the Schedule of Activities for data to be collected at the time of treatment discontinuation and follow-up and for any further evaluations that can be completed

In the case of pregnancy, the investigator must immediately notify the Sponsor or designee of this event. In most cases, the study drug will be permanently discontinued in an appropriate manner (eg, dose tapering if necessary for participant safety). Please contact the Sponsor or designee within 24 hours of awareness of the pregnancy. If the investigator determines a possible favorable benefit/risk ratio that warrants continuation of study drug, a discussion between the investigator and the Sponsor or designee must occur.

All participants who discontinue study treatment should comply with protocol specified follow-up procedures as outlined in [Section 2](#). The only exception to this requirement is when a participant withdraws consent for all study procedures including post-treatment study follow-up or loses the ability to consent freely (i.e., is imprisoned or involuntarily incarcerated for the treatment of either a psychiatric or physical illness).

If study treatment is discontinued prior to the participant's completion of the study, the reason for the discontinuation must be documented in the participant's medical records and entered on the appropriate case report form (CRF) page.

The assessment for discontinuation of nivolumab should be made separately from the assessment made for discontinuation of ipilimumab. Although there is overlap among the discontinuation criteria, if discontinuation criteria are met for ipilimumab but not for nivolumab, treatment with nivolumab may continue if ipilimumab is discontinued.

If a participant in any of the nivolumab/ipilimumab combination cohorts meets criteria for discontinuation and investigator is unable to determine whether the event is related to both or one study drug, the participant should discontinue both nivolumab and ipilimumab and be taken off the treatment phase of the study.

